### 5.4. PER PROTOCOL ANALYSIS SET [PPAS]

No per protocol analysis set (PPAS) is defined in this trial.

### 5.5. SAFETY ANALYSIS SET [SAF]

The safety analysis set (SAF) will contain all subjects who received at least one dose of trial medication during the 1297.3 trial. Subjects will be classified according to randomized / re-randomized treatments received in trial 1297.2.

If there is any doubt whether a subject was treated or not, they will be assumed treated for the purposes of analysis. Subjects will be classified according to randomized / re-randomized treatments group allocated in trial 1297.2 safety outputs.

### 5.6. PHARMACOKINETIC FULL ANALYSIS SET [PKFS]

The pharmacokinetic full analysis set PKFS analysis set for the summary of PK concentrations consists of all subjects who receive at least one dose of trial medication and have at least one post-treatment valid PK concentration value.

The following are considered as non-valid PK concentration measurement:

- Sampling date or time missing
- Dosing date or time missing
- No valid result (NOR), No sample available (NOS), Not Analyzed (NOA)

---

Document: \\ieedc-nas01a\BIOSdata\Boehringer\_Ingelheim\BI\_695501\NVA96235\Biostatistics\Documentation\SAP\10  
v1.0\BI\_1297.3\_SAP\_22JUN2016\_v1.0

Author: Version Number: 1.0  
Version Date: 22JUN2016

Template No: CS\_TP\_BS016 – Revision 3  
Effective Date: 01May2012

Reference: CS\_WI\_BS005

## 6. GENERAL CONSIDERATIONS

### 6.1. REFERENCE START DATE AND STUDY DAY

Study Day will be calculated from the reference start date, and will be used to show start/stop day of assessments and events.

Reference start date is defined as the day of the first dose of trial medication in 1297.3 trial, (Day 1 is the day of the first dose of trial medication), or for subjects assigned to treatment but not treated it is the day of treatment assignment. This will appear in every listing where an assessment date or event date appears.

- If the date of the event is on or after the reference date then:

Study Day = (date of event – reference date) + 1.

- If the date of the event is prior to the reference date then:

Study Day = (date of event – reference date).

In the situation where the event date is partial or missing, the date will appear partial or missing in the listings, and Study Day, and any corresponding durations will be presented based on the imputations specified in Appendix 2; Partial Date Conventions.

### 6.2. BASELINE

Unless otherwise specified, baseline in Trial 1297.3 is defined as the last non-missing measurement taken prior to reference start date (including unscheduled assessments). In the case where the last non-missing measurement and the reference start date coincide, that measurement will be considered pre-baseline. Adverse Events (AEs) and medications commencing on the reference start date will be considered post-baseline.

For the analysis referring to the 1297.2 baseline, the baseline value as derived in 1297.2 will be used. All endpoints will be assessed using the 1297.2 baseline values. In addition, the following further endpoints will be assessed using the 1297.3 baseline values:

- DAS28 (ESR)
- ACR20 response criteria
- SF-36 v2

---

Document: \\ieedc-nas01a\BIOSdata\Boehringer\_Ingelheim\BI\_695501\NVA96235\Biostatistics\Documentation\SAP\10)v1.0\BI\_1297.3\_SAP\_22JUN2016\_v1.0

Author: Version Number: 1.0  
Version Date: 22JUN2016

Template No: CS\_TP\_BS016 – Revision 3  
Effective Date: 01May2012

Reference: CS\_WI\_BS005

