### **7.3 PLANNED ANALYSES**

All patients treated with at least one dose of trial medication during the 1297.3 trial (Safety Analysis Set) will be included in the safety evaluations.

The Full Analysis Set (FAS) will be the basis for efficacy analyses. The FAS consists of all patients who received at least one dose of trial medication in Trial 1297.3 and had at least one DAS28 (ESR or CRP) or ACR20 measured during the 1297.3 trial.

The “All Enrolled Patients” analysis set will include all patients who provide informed consent for this trial.

For presentation of results in the report, three groups of patients will be created depending on treatments assigned in Trial 1297.2. The first group will consist of patients who were randomized to BI 695501 in Trial 1297.2 and will continue to receive BI 695501 in Trial 1297.3 but via self-administration. The second group will consist of patients who were initially randomized to receive US-licensed Humira® in Trial 1297.2, continue to receive US-licensed Humira® after Week 24 re-randomization in Trial 1297.2 and will transition to BI 695501 via self-administration in the Trial 1297.3. The third group will consist of patients who were initially randomized to receive US-licensed Humira® in Trial 1297.2, transitioned to BI 695501 following the re-randomization at Week 24 in the Trial 1297.2 and continue to receive BI 695501 in Trial 1297.3 but via self-administration. [Table 7.3: 1](#) gives an overview of the above-defined patient groups.

Table 7.3: 1 Patient groups for presentation of analysis results

| Patient group                              | 1  | 2            | 3            |
|---|-----------|---------------------|---------------------|
| Randomized treatment in Trial 1297.2              | BI 695501 | US-licensed Humira® | US-licensed Humira® |
| Re-randomized treatment in Trial 1297.2 (Week 24) | BI 695501 | US-licensed Humira® | BI 695501           |

The descriptive statistics for safety, efficacy and other endpoint will be presented for these three groups and overall for all patients combined.

Unless otherwise specified, baseline for this trial (1297.3) is defined as the baseline of Trial 1297.2 and all endpoints are those assessed in Trial 1297.3.

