## 8. OUTPUT PRESENTATIONS

APPENDIX 1 shows conventions for presentation of data in outputs, unless other specified within the document (e.g. plasma concentration). In particular, for presentation of results, three groups of patients will be created depending on treatments assigned in Trial 1297.2.

The templates provided with this SAP describe the presentations for this trial and therefore the format and content of the summary tables, figures and listings to be provided by Biostatistics.

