#### **15.2.1.2. ACR20 endpoint**

A secondary efficacy endpoint is

- The proportion of subjects meeting the ACR20 response criteria (based on improvement since Baseline in trial 1297.2) at Week 48 of trial 1297.3.

ACR20 response will be calculated at every planned efficacy assessment visit.

A subject has an ACR20 response if all of the following occur:

- A  $\geq 20\%$  improvement in the swollen joint count (66 joints)
- A  $\geq 20\%$  improvement in the tender joint count (68 joints)
- A  $\geq 20\%$  improvement in at least three of the following assessments:
  - Patient's assessment of pain
  - Patient's global assessment of disease activity
  - Physician's global assessment of disease activity (see below for more details).
  - Patient's assessment of physical function, as measured by the Health Assessment

---

Document: \\ieedc-nas01a\BIOSdata\Boehringer\_Ingelheim\BI\_695501\NVA96235\Biostatistics\Documentation\SAP\10\\v1.0\BI\_1297.3\_SAP\_22JUN2016\_v1.0

Author: Version Number: 1.0  
 Version Date: 22JUN2016

Template No: CS\_TP\_BS016 – Revision 3  
 Effective Date: 01May2012

Reference: CS\_WI\_BS005

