## Questionnaire – Disability Index (HAQ-DI)

- Acute phase reactant (CRP).

Improvement is assessed as the decrease in a component relative to baseline,  $(100 \times (\text{baseline} - \text{post baseline}) / \text{baseline})$ .

The handling of retests, unscheduled and end of trial measurements is described in Section 6.3.

If a joint evaluation is missing or 'Not done' at baseline (please refer to section 6.2 for baseline definition), it will not contribute to the joint counts at baseline and all subsequent visits (i.e., will be treated as 'Not Done'). If at least half but not all joints are evaluable (at least 33 joints for the 66 joint count for swelling with eCRF values 'present' or 'absent', at least 34 joints for the 68 joint count for tenderness with eCRF values 'present' or 'absent'), then the observed prorated tender/swollen joint count will be calculated.

The prorated scores will be evaluated based upon the number of evaluable joints: the counted score will be multiplied by 66 for swelling or 68 for tender joint count and divided by the number of joints evaluated. For example, for tender joint count, if only 45 of the 68 joints are assessed at a visit and 18 of those 45 are tender (eCRF value 'present'), the prorated tender joint count is  $18/45 \times 68 = 27.2$ . This exact value, 27.2 (and not 18) will be used for ACR20 score calculation. For swollen joint count, if only 45 of the 66 joints are assessed at a visit and 18 of those 45 are swelling (eCRF value 'present'), the prorated swollen joint count is  $18/45 \times 66 = 26.4$ . This exact value, 26.4 (and not 18) will be used for ACR20 score calculation.

If less than half of the joints are evaluable (eCRF value 'not done' or missing), the number of tender/swollen joints is missing.

The central laboratory data for CRP and eCRF data for all other ACR20 components will be used for the calculation.

Patient's assessment of pain as well as patient's and physician's global assessment of disease activity accessed using the VAS of 100 mm.

**Patient's assessment of physical function** will be assessed using HAQ-DI. The calculation of this index is described below. The HAQ-DI is composed of 20 items. There are eight categories, each of which has at least two component questions:

1. Dressing and grooming
2. Arising
3. Eating
4. Walking
5. Hygiene
6. Reach
7. Grip
8. Common daily activities.

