#### 15.2.1.3. ACR/EULAR remission

A secondary efficacy endpoint is

- The proportion of subjects who meet the ACR/EULAR definition of remission (based on improvement since Baseline in trial 1297.2) at Week 48 of trial 1297.3.

To have the ACR/EULAR Remission, the subject must satisfy all of the following criteria:

- Tender joint count (TJC) (68)  $\leq$  1
- Swollen joint count (SJC) (66)  $\leq$  1
- CRP  $\leq$  1mg/dL
- Patient global assessment  $\leq$  10 (on a 0-100 scale)

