# lost to follow-up from trial is also included here, or patients who took a therapy that may significantly impact efficacy assessment prior to this time-point.

The following steps will be followed:

Step 1: Missing ACR20 component data will be imputed using the last observation carried forward (LOCF) method

Document:	\\ieedc-nas01a\BIOSdata\Boehringer_Ingelheim\BI_695501\NVA96235\Biostatistics\Documentation\SAP\10\v1.0\BI_1297.3_SAP_22JUN2016_v1.0	Version Number:	1.0
Author:		Version Date:	22JUN2016

Template No: CS\_TP\_BS016 – Revision 3  
 Effective Date: 01May2012

Reference: CS\_WI\_BS005

and ACR20 will be calculated based on the imputed component data.

Last observation will be carried forward as many time as needed.

Step 2: The imputed ACR20 will be set to non-responder at Week 48, if the subject

- discontinue treatment prior to Week 48
- are lost-to-follow-up prior to Week 48
- have any severe violation related to any therapy that may significantly impact efficacy assessment prior to Week 48

Severe violation related to any therapy (according to CTP Table 4.2.2.1: 1) that may significantly impact efficacy assessment will be assessed by:

- providing to the trial medical advisor
  - a list of medication codes (WHO Drug Dictionary version SEPR2015 or higher) presented in CTP Table 4.2.2.1: 1 and taken by at least one subject during trial conduct.
  - full individual concomitant medication information including dose, frequency and Study day at start of medication.
- Trial medical advisor will then identify the medications and start date of severe violation which may impact efficacy assessment

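### Is ACR20 against the 1297.3 baseline a faulty summary because a patient who merely holds steady counts as a non-responder?

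*SAP*

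**What the plan says.** Protocol 7.3 sets the default: unless otherwise specified, "baseline for this trial (1297.3) is defined as the baseline of Trial 1297.2". SAP 6.2 follows it for all endpoints and then adds a short list: "In addition, the following further endpoints will be assessed using the 1297.3 baseline values". The list holds DAS28 (ESR), ACR20 and SF-36 v2.

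SAP 15.2.1.2 defines the criterion: "A subject has an ACR20 response if all of the following occur". The conditions are a fall of at least 20% in the 66-joint swollen count, the same in the 68-joint tender count, and the same in three of five other measures. "Improvement is assessed as the decrease in a component relative to baseline", that is, 100 × (baseline − post baseline) / baseline. "ACR20 response will be calculated at every planned efficacy assessment visit".

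The secondary endpoints in SAP 15.2.1 are anchored elsewhere. DAS28 change, ACR20 and EULAR response at Week 48 refer to the 1297.2 baseline. Remission is defined by absolute limits ("To have the ACR/EULAR Remission, the subject must satisfy all of the following criteria"), among them at most one swollen and one tender joint. For missing data, SAP 15.2.2.2 adds a non-responder rule (NRI): "The imputed ACR20 will be set to non-responder at Week 48, if the subject" stops treatment, is lost to follow-up or has a severe therapy violation before then.

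Protocol 7.2 and SAP 6.5 plan no hypothesis test. SAP 8 leaves layout to documents outside the public copy: "The templates provided with this SAP describe the presentations for this trial". The pages after SAP 15.2.3 are blank in that copy. Protocol 5 points to a section 5.1.3 for other endpoints, and that section is not reproduced.

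**The concern.** ACR20 was built to show improvement from active disease. Here it is also applied from a starting point reached after 48 weeks of treatment (Protocol 2.1). A patient who arrives well controlled and stays so cannot respond, and a patient with no swollen and no tender joints at entry has no computable ratio. Stable control, mild worsening and complete loss of response all fall into one non-responder category.

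Two things would be at stake. A reader could take a low rate as evidence that efficacy faded during the extension. And the question most natural in a long-term trial, who kept response and who lost it, would be answered better by a two-way table of ACR20 status at entry by status at Week 48, both against the 1297.2 baseline.

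**Working it through.** **The SAP's own figures.** The pro-rating examples in SAP 15.2.1.2 reproduce: 18/45 × 68 = 27.2 tender joints and 18/45 × 66 = 26.4 swollen joints.

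**Unchanged counts.** For any entry count b > 0, improvement is 100 × (b − b)/b = 0%, below 20%. Pro-rating does not change this. A joint not evaluated at baseline is dropped later, so the number of evaluable joints can only stay the same or fall, and an unchanged observed count can only pro-rate to the same value or higher. Response needs at least 1 joint fewer from an entry count of 1 to 5, 2 fewer from 6 or 10, and 4 fewer from 20. For b = 0 the denominator is zero and the ratio is undefined.

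**Within the remission limits.** With swollen and tender counts each 0 or 1, there are 4 × 4 = 16 transitions from entry to Week 48 (swollen/tender):
- entry 1/1: 3 non-response, 1 that can respond (to 0/0);
- entry 1/0: 2 non-response, 2 undefined;
- entry 0/1: 2 non-response, 2 undefined;
- entry 0/0: 4 undefined.

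The total is 7 non-response, 8 undefined and 1 possible response. If a rise from zero is read as not improved, it is 12, 3 and 1.

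**Ceiling under an assumption.** Suppose entry and Week 48 are exchangeable and undefined ratios count as non-response. Response needs the swollen count to fall, and the same event with the visits swapped needs it to rise. The two are disjoint and equally likely, so the rate cannot exceed 50%. If 10% are set to non-response by NRI (assumed), the limit is 50% × (1 − 0.10) = 45%. The actual rate cannot be computed, because the documents give no joint counts at 1297.3 entry.

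**What the visible outputs show together.** Assume swollen/tender counts of 15/25 at the 1297.2 baseline and 3/4 at 1297.3 entry, with the other ACR components met. For DAS28, assume also that all affected joints lie within the 28 and that ESR and patient global are unchanged. The DAS28 shift is then 0.56 × (√T − √4) + 0.28 × (√S − √3), with T tender and S swollen joints at Week 48.

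| Week 48 (S/T) | Improvement vs 1297.2 | ACR20 vs 1297.2 | Improvement vs 1297.3 | ACR20 vs 1297.3 | DAS28 shift since entry |
|---|---|---|---|---|---|
| 3/4, stable | 80% / 84% | yes | 0% / 0% | no | 0 |
| 5/7, somewhat worse | 67% / 72% | yes | −67% / −75% | no | +0.50 |
| 14/24, response lost | 7% / 4% | no | −367% / −500% | no | +2.19 |
| 2/3, further gain | 87% / 88% | yes | 33% / 25% | yes | −0.24 |

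The 1297.3-baseline ACR20 separates only the last row from the rest, as its definition implies. The secondary ACR20 identifies lost response, and DAS28 against the 1297.3 baseline separates all four rows. Both are in the visible plan.

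**What they do not show.** With ACR20 rates p0 at entry and p1 at Week 48 against the 1297.2 baseline, gain minus loss equals p1 − p0 exactly. Gross loss is only bounded, between max(0, p0 − p1) and min(p0, 1 − p1). With an assumed 70% at both visits and 300 patients, the upper bound is 0.30 × 300 = 90. At 60% it is 0.40 × 300 = 120, and at 80% it is 0.20 × 300 = 60.

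**The case for a change.** The strongest case for a defect runs as follows. The trial's objective includes long-term efficacy. One of the three groups moves from Humira to BI 695501 at entry, so loss of response is of direct interest there. The 1297.3-baseline ACR20 merges states that matter. The two marginal rates leave gross loss open by up to 90 of 300 patients in the example, and DAS28 change does not count lost ACR20 responses. ACR20 is derived at every efficacy visit, so a two-way table needs no new data.

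The arithmetic stands, and so does the point that marginal rates do not fix gross loss. The step from there to an error does not.

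- The ratio measures change from whichever baseline is named. Measured from 1297.3 entry it describes further improvement since entry, which is a legitimate descriptive question. The visible text claims no more for it.
- No cross-table is visible, but it cannot be called missing. It would belong on the blank pages after SAP 15.2.3, in the templates, or under Protocol 5.1.3. The same holds for a rule on zero counts or a table title.
- Swapping this output for a two-way table would drop the further-improvement summary. It might also remove something Protocol 5.1.3 requires, while SAP 3.3 records no departure from the protocol.
- The two-way table has weaknesses of its own. Under an assumed bivariate-normal response with a stable rate of 60–80% and correlation 0.5–0.9, only 73–94% of entry responders remain responders with no group-level loss, by regression to the mean. If 10% are independently set to non-response by NRI, which acts at Week 48 and not at entry, this becomes 66–84%.

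The figure of 4,622 non-responses among the 67 × 69 = 4,623 possible unchanged count pairs adds nothing: it says that 0% is below 20%, and it counts pairs, not patients.

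**Conclusion.** The concern does not hold. That an unchanged non-zero joint count is non-response is exact, but it is a property of ACR20 from a treated baseline and not a fault in the plan. Followed as written, the plan supports the conclusions it sets out to draw. The secondary endpoints do not depend on the 1297.3 baseline, the additional ACR20 is descriptive, and DAS28 (ESR) from the same entry point shows whether patients held steady or worsened. The effect on any planned conclusion is nil.

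What remains is a preference for an extra display that would split net change into gross loss and gain. Its possible yield is the 0 to 90 of 300 range above, at an assumed 70% response at both visits, against the drawbacks of regression to the mean and one-sided NRI.

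This rests on two conditions: that the report reads the 1297.3-baseline ACR20 as further improvement since entry, which is all its definition supports, and that nothing in the unpublished pages presents it as maintained response. The public documents give no reason to doubt either.

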## 6.3. RETESTS, UNSCHEDULED VISITS AND EARLY TERMINATION DATA

In general, for by-visit summaries, data recorded at the nominal visit will be presented. In the case of a retest, an unscheduled assessment will be created. For laboratory assessments, the latest available measurement within 2 days after the planned assessment will be used for by-visit summaries.

Unscheduled measurements will not be included in by-visit table summaries and by-visit graphs, but will contribute to the last observation carried forward (LOCF) values.

Treatment Early termination data will not be included in by-visit table summaries and by-visit graphs, but will contribute to the last observation carried forward (LOCF) values and be present in the listing and individual data graphs.

Listings will include all scheduled, unscheduled, retest and early discontinuation data collected in the eCRF database.

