#### **7.3.4 Safety analyses**

Adverse events will be coded using the MedDRA coding dictionary. Standard BI summary tables and listings will be produced. All AEs with an onset between start of treatment and end of the residual effect period (REP), a period of 10 weeks after the last dose of trial medication, will be assigned to the treatment period for evaluation.

All treated patients will be included in the safety analysis. In general, safety analyses will be descriptive in nature and will be presented by MedDRA system organ class and preferred term. No hypothesis testing is planned.

Statistical analysis and reporting of AEs will concentrate on treatment-emergent AEs. To this end, all AEs occurring between start of treatment and end of the REP will be considered 'treatment-emergent'. Adverse events that start before first drug intake and deteriorate under treatment will also be considered as 'treatment-emergent'.

Frequency, severity, and causal relationship of AEs will be tabulated by system organ class and preferred term after coding according to the current version of the MedDRA.

In addition, for infections/serious infections, hypersensitivity reactions, drug-induced liver injury (DILI) and injection-site reactions, patient incidence and/or event incidence per 1000 patient-years exposure will be displayed.

Laboratory values taken after the first dose of trial medication up to a period of 10 weeks after the last dose of the trial medication will be assigned to the treatment phase for evaluation. Laboratory data will be analyzed both quantitatively as well as qualitatively. The latter will be done via comparison of laboratory data to their reference ranges. Values outside the reference range as well as values defined as clinically relevant will be highlighted in the listings. Treatment groups will be compared descriptively with regard to distribution parameters as well as with regard to frequency and percentage of patients with abnormal values or clinically relevant abnormal values.

Vital signs (blood pressure, pulse rate, respiratory rate and body temperature), physical examinations, 12-lead ECGs, or other safety-relevant data observed at screening, baseline, during the course of the trial and at the end-of-trial evaluation will be assessed with regard to possible changes compared to findings before start of treatment.

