## 16.3. LABORATORY EVALUATIONS

Results from the central laboratory will be included in the reporting of this trial for Serum Chemistry, Hematology and Urinalysis. A list of laboratory assessments to be included in the outputs is included in APPENDIX 4.

Presentations will use SI and US Units.

Quantitative laboratory measurements reported as "< X", i.e. below the lower limit of quantification (BLQ), or "> X", i.e. above the upper limit of quantification (ULQ), will be converted to X for the purpose of quantitative summaries, but will be presented as recorded, i.e. as "< X" or "> X" in the listings.

Qualitative laboratory urinalysis results measured by central laboratory will be classified to the categories "Positive" and "Negative" based on the central laboratory normal reference.

The handling of retests, unscheduled and end of trial measurements is described in Section 6.3. However, laboratory values taken after the first dose of trial medication up to a period of 10 weeks after the last dose of the trial medication will be assigned to the treatment phase for evaluation. All available data will be listed.

The following summaries will be provided for laboratory data:

- Actual and change from baseline in trial 1297.2 by visit (for quantitative measurements)

---

Document: \\ieedc-nas01a\BIOSdata\Boehringer\_Ingelheim\BI\_695501\NVA96235\Biostatistics\Documentation\SAP\10  
v1.0\BI\_1297.3\_SAP\_22JUN2016\_v1.0

Author: Version Number: 1.0  
Version Date: 22JUN2016

Template No: CS\_TP\_BS016 – Revision 3  
Effective Date: 01May2012

Reference: CS\_WI\_BS005

- Shifts in Rheumatology Common Toxicity Criteria (RCTC) grading, from baseline in trial 1297.2 by visit (for gradable parameters, see APPENDIX 4)
- Shifts from baseline category (Low/ Normal/ High) in trial 1297.2 by visit (for non-gradable parameters except urinalysis parameters and ADA)
- Shift from baseline category (Negative/ Positive) in trial 1297.2 by visit (for urinalysis non-gradable parameters)
- Box plots for ESR, CRP, hemoglobin, leukocytes (equivalent to white blood cells), platelets, AST, ALT, bilirubin, creatinine, cholesterol
- Plots for time course of gradable safety parameters for subjects having at least one value with toxicity grade 3 or 4 (RCTC grading is described section 16.3.3)
- Proportion and frequency of possible Hy's law subjects
- Proportion and frequency of possible Drug Induced Liver Injuries

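### The laboratory shift tables leave out unscheduled and early-termination values, so they can understate a patient's worst on-treatment grade

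*SAP*

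**What the plan says.** SAP 6.3 sets the rules for values that do not come from a planned visit:

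- Retests: "In the case of a retest, an unscheduled assessment will be created".
- Unscheduled values: "Unscheduled measurements will not be included in by-visit table summaries and by-visit graphs".
- Early stoppers: "Treatment Early termination data will not be included in by-visit table summaries and by-visit graphs".
- Laboratory values in particular: "the latest available measurement within 2 days after the planned assessment will be used for by-visit summaries".

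SAP 16.3 adopts these rules for laboratory data: "The handling of retests, unscheduled and end of trial measurements is described in Section 6.3". It then lists three kinds of shift table, all by visit. The toxicity table is described as "Shifts in Rheumatology Common Toxicity Criteria (RCTC) grading, from baseline in trial 1297.2 by visit"; the others shift Low/Normal/High categories and, for urinalysis, Negative/Positive.

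The period of interest is wider than the planned visits. SAP 16.3, like protocol 7.3.4, assigns to the treatment phase "laboratory values taken after the first dose of trial medication up to a period of 10 weeks after the last dose of the trial medication". Protocol 7.3.4 also says that groups will be compared on the "frequency and percentage of patients with abnormal values or clinically relevant abnormal values". SAP 3.3 declares no change from the protocol's analyses.

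**The concern.** The samples left out are not a random subset. Protocol 6.1 foresees extra blood samples at unscheduled visits to follow up safety findings, and protocol 6.2.3 allows unscheduled visits for safety monitoring. Patients who stop early have an end-of-treatment visit with the Week 48 assessments, laboratory tests included. These values are collected and then kept out of every shift table.

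The trial's objective begins with long-term safety, and its primary endpoint is a safety endpoint. A reader of the laboratory section will want to know how many patients reached each toxicity grade at any time on treatment. The tables listed in SAP 16.3 do not answer that.

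**Working it through.** The documents state no figure for this point, so there is nothing to reproduce. The check is mainly logical.

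**1. Planned sampling.** The protocol Flow Chart schedules post-dose laboratory tests at Weeks 12, 24, 48 (or end of treatment) and 58. The longest on-treatment gap is 48 − 24 = 24 weeks. An abnormality that appears and resolves inside a gap is seen only in an unscheduled sample.

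**2. What reaches the shift tables under SAP 6.3.**

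| Value collected in the treatment phase | In by-visit tables? |
|---|---|
| Scheduled visit, no retest | Yes |
| Scheduled visit with a retest within 2 days | One of the two values; the text does not settle which |
| Later retest or other unscheduled sample | No |
| Early-termination visit | No |

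**3. Is there another way in?** SAP 6.3 says the excluded values feed last-observation-carried-forward values. SAP 7.3 says missing safety data are not imputed unless section 16 provides for it, and SAP 16.3 specifies no such imputation for laboratory data. So they do not return.

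**4. Direction.** Let A be all of a patient's treatment-phase values and S the subset used in by-visit tables. Since S is contained in A, worst grade over S ≤ worst grade over A. This holds whichever retest value represents the visit.

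**5. Any-time counts.** In SAP 16.3 only possible Hy's law cases and possible drug-induced liver injury are counted per patient outside the by-visit layout. Patients with a grade 3 or 4 value get individual plots, without a percentage. All values are listed.

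**6. Illustration of size (every input below is assumed except N = 300 to 400, from protocol 7.7).** Let u be the share of affected patients whose only abnormal value is unscheduled or from early termination. Let r be the share of the others who are retested within 2 days, and b the chance that such a retest is back within the threshold. If a retest replaces the scheduled value:

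captured share = 1 − u − (1 − u) × r × b

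If retests are excluded, r = 0 and the share is 1 − u. Suppose 5% of patients truly have a graded value, which is 15 of 300 or 20 of 400.

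| u | r | b | Captured share | Shown of 15 | Shown of 20 |
|---|---|---|---|---|---|
| 0.10 | 0 | – | 0.90 | 13.5 | 18.0 |
| 0.40 | 0 | – | 0.60 | 9.0 | 12.0 |
| 0.40 | 0.5 | 0.7 | 0.60 − 0.60 × 0.35 = 0.39 | 5.9 | 7.8 |

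The last row applies only under the replacement reading. For b, two normal measurements with correlation 0.5 to 0.9 were simulated. After a first value above the 95th or 99th percentile, the repeat fell to or below the cut in 36% to 87% of cases and exceeded the first value in 6% to 32%. Retests tend to fall back, but not always.

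**The case against.** **Adverse event tables cover much of this.** Protocol 5.3.3 makes a laboratory abnormality judged clinically significant an adverse event, unless it is consistent with a current diagnosis. SAP 16.1.2 and 16.1.3 tabulate treatment-emergent events, and those leading to withdrawal of the drug, with patient counts and percentages; the window runs to 70 days after the last dose. A patient who stopped because of a clinically significant result is therefore counted. This stands and narrows the gap, but those counts depend on the investigator's judgement and carry no worst laboratory grade.

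**By-visit tables do not claim to give any-time incidence.** Protocol 7.3.4 does not say that its percentage is any-time, and early stoppers still contribute the visits they attended. Both points are true. But the protocol and SAP define a treatment phase for laboratory values, and no listed shift table summarises it.

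**SAP 16.3 may intend an exception.** Its treatment-phase sentence follows the reference to 6.3 as a qualification. It assigns values to a phase without saying which table uses them. SAP section 8 leaves format and content to templates that are not in the public documents, so the gap can be asserted only for the text of 16.3.

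**Stronger readings a reader might infer.**

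- That a normal retest overwrites the abnormal result. This is one reading of an inconsistent section; on the other, the retest is excluded and the original stays. The rule takes the latest value, not the lowest, so a worse retest could also replace a milder one. The one repeat interval given, 48 to 72 hours for liver alerts in protocol 10.5, mostly falls outside 2 days.
- That every visit percentage is biased downwards. Early stoppers leave the denominator as well as the numerator, so this does not follow.
- That 30 to 60 patients are affected. This is 10% of 300 to 15% of 400, but the documents give no discontinuation rate, and it counts patients with any end-of-treatment value, not abnormal ones.

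**Conclusion.** The point holds for worst grade per patient. The tables listed in SAP 16.3 can equal or fall below the true worst on-treatment grade, never exceed it, and they supply no any-time percentage of patients with abnormal values outside Hy's law and drug-induced liver injury. The retest sentences in SAP 6.3 contradict each other and need reconciling.

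Harm is not hidden from the report as a whole. The gap is mainly worst grade per patient and abnormalities not reported as adverse events. Its size cannot be derived from the documents; the captured shares of 39% to 90% above only show how the result moves with assumed inputs. The conclusion rests on the SAP text, without the table templates.

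**What to change.** - **SAP 16.3:** add a shift table from the 1297.2 baseline to the worst on-treatment RCTC grade. For non-gradable parameters, use the worst Low or High category, or Positive for urinalysis. Give the number and percentage of patients with any abnormal value. Use all scheduled, retest, unscheduled and early-termination values from first dose to last dose + 70 days.
- **SAP 6.3:** reconcile the retest sentences by stating that the original scheduled value represents the visit and that retests enter the worst-value table. The by-visit tables otherwise stay as planned.

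The cost is one extra table per laboratory panel and slightly less favourable reported abnormality rates. No new data are needed.
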